# 11 PHARMACOKINETICS AND LABORATORY ANALYSES

[figure not shown]
# 11.1 Blood pharmacokinetics of Pexa-Vec

# 11.2 Blood pharmacokinetics of nivolumab

# 11.3 Other laboratory analyses

### 12 STATISTICAL METHODS PLANNED AND SAMPLE SIZE

## 12.1 Determination of sample size

## **Hypothesis**

As the patient survival benefit may be correlated with either radiological response of tumors or/and prolonged stabilization of the disease, the analysis of efficacy will consider ORR as primary endpoint. Sample size justification will use available data on ORR, as such: in a Phase I/II trial, 8/42 (19%) patients with previously treated HCC experienced an objective response when treated with single-agent nivolumab (El-Khoueiry et al., ASCO 2015). Therefore, a response rate of 15%-20% with the combination of Pexa-Vec + nivolumab in these patients would be considered disappointing, while a response rate of 35% or more would be promising and would encourage further study of the regimen in these patients. The null hypothesis for response rate H0 is set at 15%, the alternate hypothesis of efficacy is set at HA=35%, the type I error α is set at 5% one sided and the power is set at 80%.

## Statistical Design

Under these hypotheses a two-stage group sequential design using alpha and beta spending function approach with Lan DeMets spending function (O'Brien-Fleming efficacy boundaries and non-binding Pocock futility boundaries) will be used leading to a maximum sample size of 30 evaluable patients and an interim analysis based on 15 evaluable patients (implemented in EAST® 6.3) with a test proportion with normal approximation to the binomial distribution. In the first stage 15 evaluable patients will be accrued. If there are 3 or fewer responses in these 15 patients (20% of responders or less), the study could be stopped for futility. If there are 6 or more responses in these 15 patients (40% of responders or more), the null hypothesis will be rejected and the study could be stopped. Otherwise 15 more additional evaluable patients will be accrued for a total of 30.

At the final analysis, the null hypothesis will be rejected if 8 or more responses are observed in the 30 evaluable patients (26.7% of responders or more) with a power of 80% and a type I error of 5%. It should nevertheless be reminded that given the mechanism of action of the drugs involved and the effects of immunotherapy on tumor behavior, ORR may not be the best measure of anti-tumor activity. For this reason, consideration will be given to DCR, TTP and survival parameters prior to deciding that the combination does not warrant further exploration. At interim and final analysis, enough patients will be treated to obtain a total of 15 and 30 evaluable patients, respectively including comparable patients of the Phase I part (population, treatment regimen) still evaluable for Phase II part.

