## 7.3.3 Stopping Rules

If there are 3 or fewer responses in these 15 patients (20% of responders or less), the study could be stopped for futility. If there are 6 or more responses in these 15 patients (40% of responders or more), the null hypothesis will be rejected and the combination will be considered to have a substantial activity to be of further interest and the study could be stopped for efficacy. Otherwise 15 additional evaluable patients will be accrued for a total of 30.

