## 8 STATISTICAL METHODS

## 8.1 General principles

Statistical summaries will be produced using SAS® software version 9.4. The tables, listings and graphics will be prepared in landscape format.

Continuous variables will be described using: number of observations (N), arithmetic mean (Mean), standard deviation (sd), minimum (MIN), median (Median), the interquartile range (Q1-Q3) and maximum (MAX). One additional decimal point for mean, median, Q1 and Q3, and 2 additional decimal points for sd will be used. Data with more than 3 decimal places (if any), may not follow this rule: so 3 decimal places will be used.

Categorical variables will be presented using the number of observations (N) and percentages (%). Proportions will be displayed with one decimal and estimated with their exact (Clopper-Pearson) 95% CIs when appropriate.

All statistical testing will be two-sided at the 0.05 level without adjustments for multiplicity testing, unless specified otherwise. P-values will be presented to 3 decimal places. Any p-value less than 0.001 will be presented as <0.001, even if it would normally round up to 0.001.

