## 8.7.1 Primary efficacy endpoint and analysis

For Phase IIa part the primary endpoint is the Overall response rate (ORR) which is the proportion of patients, whose best overall response is either CR or PR, confirmed at least 4 weeks after initial documentation. A test proportion with normal approximation to the binomial distribution will be used and null hypothesis will be rejected if 8 or more responses are observed in the 30 evaluable patients (26.7% of responders or more)

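### The two-stage Phase IIa rule (reject at 6 or more of 15, or 8 or more of 30) has an exact one-sided type I error of 7.4%, or 5.5% if the futility stop is always followed, not the stated 5%

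*Protocol*

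**What the plan says.** Protocol section 12.1 (Hypothesis), repeated in the synopsis and in SAP section 7.1, sets the hypotheses ("The null hypothesis for response rate H0 is set at 15%, the alternate hypothesis of efficacy is set at HA=35" per cent) and the targets ("the type I error α is set at 5% one sided and the power is set at 80" per cent). The design is Lan-DeMets with "O'Brien-Fleming efficacy boundaries and non-binding Pocock futility boundaries", 30 evaluable patients at most and one look at 15, using a one-sample proportion test with a normal approximation.

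The resulting counts are:

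- **Futility:** 3 or fewer responses in 15. The wording is permissive, so stopping is optional.
- **Interim efficacy** (SAP section 7.3.3): "If there are 6 or more responses in these 15 patients (40% of responders or more), the null hypothesis will be rejected".
- **Final:** "At the final analysis, the null hypothesis will be rejected if 8 or more responses are observed in the 30 evaluable patients". Protocol sections 12.1 and 12.8, the synopsis and SAP section 7.4 all attach 80% power and 5% type I error to this cut-off.

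The approximation is also the planned primary test. SAP section 8.7.1 says: "A test proportion with normal approximation to the binomial distribution will be used and null hypothesis will be rejected if 8 or more responses". For reporting, SAP section 8.1 has proportions "estimated with their exact (Clopper-Pearson) 95% CIs when appropriate". Neither document gives exact binomial operating characteristics for the rule.

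**The concern.** Under the null the expected number of responses is 15 × 0.15 = 2.25 at the interim and 30 × 0.15 = 4.5 at the end. With counts that small the binomial is skewed to the right, and a normal upper tail understates the chance of a high count. A cut-off placed by that tail is then too easy to reach.

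This is the only formal success rule for the Phase IIa primary endpoint. Readers of the protocol or the study report would take the 5% as the false-positive risk of a positive result. The provision to weigh disease control, time to progression and survival applies before the combination is abandoned, so it can rescue a negative result but does not protect against a false positive one.

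**Working it through.** **Inputs.** p0 = 0.15, p1 = 0.35, one-sided α = 0.05, power 0.80, looks at 15 and 30, futility non-binding (Protocol 12.1; SAP 7.1). Cut-offs 3/15, 6/15 and 8/30 (Protocol 12.1, 12.7, 12.8; SAP 7.3.3, 7.4).

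**Step 1: the plan's own figures under its own method.** Information fraction 15/30 = 0.5.

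- O'Brien-Fleming-type spend at the interim: 2[1 − Φ(1.960/√0.5)] = 0.0056, so z = 2.538. The final z is 1.662.
- Efficacy counts, n·p0 + z√(n·p0(1 − p0)): interim 2.25 + 2.538 × √1.9125 = 5.76, so 6. Final 4.5 + 1.662 × √3.825 = 7.75, so 8.
- Pocock-type beta spend: 0.20 × ln(1 + (e − 1) × 0.5) = 0.124. The futility count, using the variance under p1, is 3.12, so 3.
- Normal-approximation power at N = 30 with the futility boundary: 80.3%.

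The counts and the 80% are therefore reproduced, and the 5% is the nominal level of that approximation.

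**Step 2: exact error of the same rule.** Let X1 and X2 be independent Binomial(15, p). Then

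P(reject) = P(X1 ≥ 6) + Σ(x = 0 to 5) P(X1 = x) × P(X2 ≥ 8 − x).

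If futility is always followed, the terms x = 0 to 3 drop out. At p = 0.15:

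| x | P(X1 = x) | P(X2 ≥ 8 − x) | product |
|---|---|---|---|
| 0 | 0.08735 | 0.00061 | 0.00005 |
| 1 | 0.23123 | 0.00361 | 0.00083 |
| 2 | 0.28564 | 0.01681 | 0.00480 |
| 3 | 0.21843 | 0.06171 | 0.01348 |
| 4 | 0.11564 | 0.17734 | 0.02051 |
| 5 | 0.04490 | 0.39577 | 0.01777 |

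The products sum to 0.05744, of which x = 0 to 3 give 0.01917 (unrounded terms). P(X1 ≥ 6) = 0.01681.

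- Futility ignored: 0.01681 + 0.05744 = 0.0743, or 7.4%.
- Futility followed: 0.0743 less 0.0192 = 0.0551, or 5.5%.

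At p = 0.35 the same sum gives 0.879 with futility ignored and 0.783 with it followed.

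**Step 3: where the gap arises.**

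- At 8/30, z = (0.2667 − 0.15)/√(0.15 × 0.85/30) = 1.790, normal p = 0.037. Exact P(X ≥ 8 | 30, 0.15) = 0.070.
- At 6/15, normal p = 0.0033, exact 0.0168. That is three times the planned interim spend (0.0168/0.0056 = 3.0).
- The exact one-sided 95% lower limit at 8/30 is 14.0%, so at the same α the exact limit does not exclude 15%.

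**Step 4: alternatives at N = 30, same enumeration.**

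| Efficacy / final / futility | Type I error, futility ignored | Power, ignored | Power, followed |
|---|---|---|---|
| ≥6/15, ≥8/30, ≤3/15 (plan) | 7.4% | 87.9% | 78.3% |
| ≥6/15, ≥9/30, ≤2/15 | 3.7% | 78.9% | 77.6% |
| ≥6/15, ≥9/30, ≤3/15 | 3.7% | 78.9% | 72.8% |
| ≥7/15, ≥9/30, ≤2/15 | 2.9% | 77.7% | 76.4% |

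**The case against.** The best defence is that the method is disclosed, the counts follow from it, and the 5% is a correct nominal value in a study the protocol itself calls exploratory. The first two parts stand: this is no slip of arithmetic. They do not rescue the statement, because the documents present 5% as the error of the rule, and the actual error of a rule on 30 binary outcomes can be calculated exactly. A second defence is that 5.5% is close to 5%. It is, but it applies only if the futility stop is always obeyed. With a non-binding boundary and permissive stopping language, type I error is properly assessed with futility ignored.

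A reader might infer more than the documents support:

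- **That 8/30 by itself has a 7.4% error.** As a single-stage rule it has 7.0%; 7.4% belongs to the two-stage procedure.
- **That the stated power is wrong.** 78.3% with futility followed is within two points of 80%, and 87.9% is above it. This is not a separate defect.
- **That the reported 95% interval contradicts the test.** A two-sided 95% interval corresponds to a one-sided 2.5% test and need not agree with a 5% one. At 8/30 it is 12.3% to 45.9%, but even at 9/30 it starts at 14.7%. Only the one-sided 95% limit (the 90% interval) is a fair comparison.
- **That the futility look loses 17.3 points of power.** That is the chance of 3 or fewer of 15 at a true rate of 35%. Many of those trials would fail anyway; the loss is 87.9 − 78.3 = 9.6 points.
- **That success rates at a true 20% show further type I error.** The protocol does say that "a response rate of 15%-20% with the combination of Pexa-Vec + nivolumab in these patients would be considered disappointing", but that bears on the choice of a 15% null, a separate matter.

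**Conclusion.** The stated 5% does not describe the primary decision rule. At a true response rate of 15% the exact one-sided error is 7.4% in the governing case (7.4/5 ≈ 1.5 times the claim) and 5.5% if futility is always followed. Each belongs with its own power at 35%: 87.9% and 78.3% respectively. No reading of the rule gives 5% or less, since the final cut-off taken alone gives 7.0%. The cause is the normal approximation, which is anti-conservative at these sample sizes and this null.

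The figures assume independent responses with a common rate, looks at exactly 15 and 30 evaluable patients, and the counts applied as written.

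**What to change.** **Minimum change, wording only.** In the synopsis, Protocol sections 12.1 and 12.8, and SAP sections 7.1, 7.4 and 8.7.1:

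1. Replace the claim of 80% power and 5% type I error by both exact pairs: 7.4% and 87.9% with futility ignored, 5.5% and 78.3% with it followed.
2. Replace the normal-approximation test by the exact binomial test. If 8/30 is kept, say that the count decides and that the procedure runs at 7.4%. An exact test at 5% would not reject at 8/30.
3. Report the exact one-sided p-value, and a 90% Clopper-Pearson interval beside the 95% one.

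This needs no patients and moves no threshold.

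**Optional change, if type I error must stay at or below 5%.** Reject at 9 or more of 30, keep 6 or more of 15 for efficacy, and set futility at 2 or fewer of 15. Exact type I error is then 3.7% (3.6% with futility followed), and the one-sided 95% lower limit at 9/30 is 16.6%, above the null. The price is one more response at the end and power of 78.9% (77.6% with futility followed), so the 80% must be restated as well. Moving only the final cut-off is a poor choice, because it leaves 72.8% when futility is followed. Protocol section 12.7 and SAP section 7.3.3 would need the same edits.

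Take this option only if no response data have yet been used. The trial is open-label. The SAP is dated December 2018 and the amended protocol March 2019, with recruitment expected to finish in February or March 2019. The interim may therefore already have taken place, although the documents do not say so. If it has, keep the counts and disclose their exact properties.

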## 12.2 Study endpoints

#### Primary endpoints

Phase I part: The primary objective is to evaluate the safety profile of intratumoral (IT) Pexa-Vec combined with intravenous (IV) nivolumab in patients with advanced HCC.

Phase IIa part: The primary objective is to evaluate the anti-tumor activity and efficacy of IT Pexa-Vec combined with IV nivolumab in patients with advanced HCC with respect to the following endpoint: Overall Response Rate (ORR) (RECIST 1.1).

# • Secondary endpoints

The secondary objectives of this study are to evaluate the efficacy of Pexa-Vec combined with nivolumab in patients with advanced HCC with respect to the following endpoints (imaging endpoints evaluated by RECIST 1.1):

- Safety (Phase IIa)
- Disease Control Rate (DCR) at 4 months
- Disease Control Rate (DCR) (proportion of non-progressing patients over time)
- Time to Progression (TTP)
- Duration of Response (DoR)
- Progression Free Survival (PFS) (median and proportion of non-progressing patients over time)
- Overall Survival (OS)(median and proportion of survivors over time)
- Blood viral load (HCV, HBV when appropriate)

## 12.3 Statistical and analytical plans

## 12.3.1 Demographic and baseline characteristics

Baseline demographics and characteristics will be listed and summarized for each phase and presented by dose.

Qualitative data (eg. Gender, Country) will be summarized by percentages and quantitative data (e.g., age and body weight) will be summarized by appropriate descriptive statistics (mean, standard deviation, median, minimum and maximum).

## 12.3.2 Safety Data

Safety data are primary endpoint for Phase I and secondary endpoint for Phase IIa. The primary dataset for safety evaluation is the safety population.

The safety data will be classified according to their intensity and relationship to the IMP. The more common AEs, laboratory test changes, etc. will be identified, classified and analyzed, as appropriate, for factors that may affect the frequency of AEs, such as time dependence, relation to demographic characteristics or relation to dose. The number of patients with each AE will be displayed by decreasing frequency of occurrence and body system classes and by SOC and preferred Term.

From the date of signature of the informed consent form and up to prior to initiation of either IMP administration, AEs, SAEs, or procedure related ARs that occur during this period, and that are considered by the investigator as relevant to the patient condition, will be collected as a current medical history and reported as such in eCRF.

All AEs occurring after the initiation of the study treatments, including events likely to be related to the underlying disease or likely to represent concomitant illness should be reported, including events present at baseline which worsened during the study. Written narratives will be provided for all serious, unexpected or other important AEs that are judged to be of special interest because of their clinical importance.

#### 12.3.3 Efficacy data

The primary dataset for efficacy evaluation is the Per Protocol population.

## Primary objectives for Phase IIa

Overall response rate (ORR) is the proportion of patients, whose best overall response is either CR or PR, confirmed at least 4 weeks after initial documentation.

# Secondary objectives for Phase I and Phase IIa

Disease control rate (DCR) is the proportion of patients whose best overall response during their participation in the study is either CR, PR, or SD. It will be presented using percentage and exact 95% confidence interval. 4-month (18-week) DCR is proportion of patients whose best overall response in the study is either CR, PR, or SD 4 months after D1.

The Time to Progression (TTP) is the time from Day 1 to the date of first documented radiographic tumor progression. TTP does not include deaths. If a patient has not had a TTP event at the cut-off date for analysis, TTP will be censored at the date of last evaluable tumor assessment before the cut-off.

Progression Free Survival (PFS) is the time from Day 1 to the date of first documented tumor progression or death due to any cause, whichever occurs first. If a patient has not had a PFS event at the cut-off date for analysis, PFS will be censored at the date of last evaluable tumor assessment before the cut-off.

Overall Survival (OS) is the time from Day 1 to the date of death due to any cause. If a patient is not known to have died at the cut-off date for analysis, survival will be censored at the date of last contact.

Duration of overall Response (DoR) applies only to patients whose best overall response is CR or PR. The start date is the date of first documented response (CR or PR) and the end date is the date of first documented disease progression or the date of death due to underlying cancer. DoR will be censored if progression or death due to underlying cancer is not observed at the cut-off date for the analysis or start of further antineoplastic therapy. The censoring date will be the date of the last evaluable tumor assessment.

TTP, PFS, OS and DoR will be presented using the number of events, number of censored patients, quartiles TTP/PFS/OS/DoR (Q1, median and Q3) and the associated confidence interval. A graphical representation will be done for these four outcomes using a Kaplan-Meier curve with 95% confidence interval.

For OS, the percent survivors over time will also be presented considering the proportions of patients alive at 6, 9, 12, 18, and 24 months, along with corresponding 95% CIs.

For PFS, the percent non-progressors over time will also be presented considering the proportions of patients having not progressed at 6, 9, 12, 18, and 24 months, along with corresponding 95% CIs.

Tumor size is defined as the sum of the diameters recorded for all target lesions as identified at baseline. Relative change from baseline in tumor size over time will be analyzed using a repeated measurements analysis model.

## Immunology data

Blood viral load (HCV, HBV when appropriate) evolution over time will be studied by considering a parametric or non-parametric (as appropriate) paired test to compare baseline value at Day 1 and value measured at Week 6.

# Exploratory efficacy analyses

# 12.4 Disposition of patients

The number of patients screened and not included will be presented with the main reason for their non-inclusion. All patients who failed to meet inclusion criteria after informed consent signature will be considered as screening failure and reported in the study report.

All patients enrolled and who completed each phase of the study will be considered in the study report. All post-inclusion discontinuations will be summarized by main reason for discontinuation.

#### 12.5 Protocol deviations

Any protocol deviation will be discussed with the Investigator on a case by case basis, and characterized as minor or major. Patients with deviations deemed major cannot be included in per protocol analyzes and should be replaced. Anticipated but not limited major deviations are:

- Failure to complete all 3 IT Pexa-Vec injections and 2 nivolumab IV infusions in the Phase I part, 2 IT Pexa-Vec injections and 2 nivolumab IV infusions in the Phase IIa part,
- No histological confirmation of HCC.
- Previous systemic therapy for HCC,
- Child-Pugh score beyond A, or deteriorated hepatic function beyond score, or advanced cirrhosis diagnosis based on albuminemia, INR, bilirubin blood levels and clinical symptoms: uncontrolled ascites or esophageal varices, etc.
- ECOG PS > 1,
- Prohibited concomitant medications or no withdrawal of anti-hypertensive, anticoagulant or anti-platelet medications within protocol-specified conditions,
- Immunologic deficiency,
- Pregnancy and breast-feeding.

## 12.6 Data sets analyzed

# Safety population

All patients entered into the study who received at least one dose of either IMP will be included in the safety analysis. The patients will be analyzed according to the treatment actually received and this population will be the primary dataset for safety evaluation.

## **DLT Population**

All patients entered into the study who received at least one dose of either IMP and who are evaluable for Phase I will be included in DLT population. The patients will be analyzed according to the treatment actually received and this dataset will be used for safety evaluation.

## Per protocol population

The main analyses will be based on a per protocol population, only including evaluable patients for Phase II and excluding all patients with major protocol deviations like eligibility deviations or deviations from protocol. Evaluable patients from Phase I who are comparable (same inclusion/exclusion criteria and same treatment regimen), still evaluable for Phase II and without major deviation will be included in the PP population. The patients will be analyzed according to the treatment planned and this dataset will be the primary dataset for efficacy evaluation.

## Intent to treat population

In addition, there will be intent to treat population, i.e. on all patients treated with at least one administration of either drugs, irrespective of the time of stopping the treatment. The patients will be included according to the treatment planned and this dataset will be used for efficacy evaluation.

A patient evaluable for Phase I assessments is an eligible patient, who completed the DLT period up to D29, including all three intratumoral injections of Pexa-vec and two infusions of nivolumab. A patient evaluable for Phase IIa assessments is an eligible patient having received at least 2 administrations of Pexa-Vec and 2 administrations of nivolumab and undertaken at least one post-baseline radiological assessment or exhibited any evidence of disease progression other than radiological. Per protocol analysis for the Phase I section should include at least 6 evaluable patients treated with the same dose level; per protocol analysis for the Phase IIa section should include at least 30 evaluable patients that may include comparable Phase I patients (population, regimen), who are evaluable for Phase IIa analysis.

